### 7.7 Retreatment Criteria for Cetuximab

Cetuximab may only be administered if all the following criteria are met regardless of cycle, providing no criteria for discontinuation are met:

- Acne-like rash is grade 2 or less
- All other grade 3 or 4 non-hematologic out-of-field toxicities (except fatigue, electrolyte abnormalities, anorexia, pain) have improved to grade 2 or less.
- For in-field toxicities see section 7.6

### 7.8 Duration of Therapy/Withdrawal from Study

Criteria for removal from study are:

- Disease progression,
- Study closure,
- Unacceptable adverse event(s) as defined in dose modification or other unacceptable AEs,
- Patient decision to withdraw from the study, or
- In the judgment of the investigator, further treatment would not be in the best interest of the patient.
- Pregnancy: Pregnant participants will continue to be followed for the duration of the pregnancy.

## 8. MEASUREMENT OF RESPONSE

Response will be evaluated in this study using the international criteria proposed by the Response Evaluation Criteria in Solid Tumors (RECIST v1.1) Committee.

### 8.1 Methods of Measurement

Imaging based evaluation is preferred to evaluation by clinical examination. The same imaging modality must be used throughout the study to measure disease.

#### CT and MRI

CT and magnetic resonance imaging (MRI) are the best currently available and most reproducible methods for measuring target lesions. Conventional CT and MRI should be performed with contiguous cuts of 10 mm or less in slice thickness. Spiral CT should be performed by use of a 5 mm contiguous reconstruction algorithm. This specification applies to tumors of the chest, abdomen, and pelvis, while head and neck tumors, and those of the extremities require specific procedures.

#### Chest X-Ray

Lesions on chest x-ray are acceptable as measurable lesions when they are clearly defined and surrounded by an aerated lung. However, CT is preferable. A chest x-ray only needs to be done if clinically indicated by the treating physician. It is not required for study purposes.

#### Tumor Markers

Tumor markers alone cannot be used to assess response. If initially above the upper normal limit, a tumor marker must return to normal levels for a patient to be considered in complete clinical response when all tumor lesions have disappeared.

#### Clinical Examination

*FOR THIS STUDY evaluation of measurable disease in the primary site by ENT examination is allowed.*

### Cytology and Histology

Cytologic and histologic techniques can be used to differentiate between complete and partial response in rare cases (e.g., after treatment to differentiate residual benign lesions and residual malignant lesions in germ cell tumors). Cytologic confirmation of the neoplastic nature of any effusion that appears or worsens during treatment is required when the measurable tumor has met response or stable disease criteria.

*The pathologic response after biopsy or neck dissection post chemoradiotherapy will be recorded.*

## 9. STUDY PARAMETERS

### 9.1 Evaluations at Screening/Baseline

(Performed within 4 weeks of registration unless otherwise indicated)

- Sign informed consent
- History and physical examination, including vital signs, weight and performance status determination (within 1 week of registration).
- Complete blood counts, including platelets (within 1 week of registration).
- Blood chemistry studies, including creatinine, electrolytes (K+, Na+, Cl-, CO2), calcium, Mg (within 1 week of registration), PT/PTT and liver function tests, including bilirubin, AST (SGOT), ALT (SGPT), and alkaline phosphatase (within 1 week of registration).
- Pregnancy (when applicable, within 3 days prior to treatment initiation) test.
- CT and/or MRI of the neck and CT of the chest and other imaging studies as indicated for staging and baseline tumor measurements. Any scans used to document measurable disease should be done as close to study entry as possible and within 4 weeks prior to registration.
- PET scan (optional)
- Bone scan (if clinically indicated)
- Dental evaluation (within 8 weeks of registration)
- ENT evaluation/endoscopy (within 8 weeks of registration)
- Swallowing assessment (within 8 weeks of registration)
- Pretreatment biopsy

### 9.2 Evaluations During Treatment

During treatment - weekly

- History and physical examination. A focused evaluation of toxicities on a weekly basis will be

performed at a minimum. A complete history and physical examination is needed at least every 3 weeks.

- CBC, platelets and creatinine/electrolytes
- Liver function tests: Bilirubin, AST (SGOT), ALT (SGPT), and alkaline phosphatase. LFTs are required every 3 weeks or more frequently if indicated.
- Vitals signs will be checked every time cetuximab is administered.
- Tumor biopsy at baseline and after 2 weeks (prior to the start of radiation).

### 9.3 Evaluations at Follow-Up

#### 2 weeks after completion of radiation treatment

- History and physical examination
- Complete blood counts, including platelets
- Blood chemistry studies, including creatinine, electrolytes (K+, Na+, Cl, CO2), Ca++, Mg++, and liver function tests, including bilirubin, AST (SGOT), ALT (SGPT), and alkaline phosphatase

#### After completion of radiation (10 +/- 2 weeks after)

- History and physical examination
- Complete blood counts, including platelets
- Blood chemistry studies, including creatinine, electrolytes (K+, Na+, Cl, CO2), Ca++, Mg++, ENT evaluation/endoscopy
- Liver function tests: Bilirubin, AST (SGOT), ALT (SGPT), and alkaline phosphatase
- CT and/or MRI of neck
- CT of chest
- Response assessment by clinical and by radiographic evaluation (reported separately) in primary and lymph nodes
- PET scan (optional)

After completing treatment, patients will be seen every 3 months for 2 years and then every 6 months for 3 years (i.e. until 5 years from radiation completion), and subsequently annually for a total of 10 years from study initiation (follow up evaluation will include assessment of late toxicities, such as dysphagia, G-tube feedings requirements, xerostomia, and others)

- CT scans of chest and head and neck will be performed every 3 months for 1 year and then every 6 months until 3 years from the completion of radiation. Then, CT of the chest will be done on an annual basis
- Swallowing assessments will be performed 3 months post radiation completion, and if problems persist, at 12 months post radiation

## 9.4 Study Parameters Table

	Baseline	During treatment and 2 weeks post RT	10 +/- 2 weeks after RT	Off therapy Follow-Up 
Study treatment (See Section 5)		X	X	
History and physical exam	X	X 	X	X
Height	X			
Weight	X	X 	X	
Vital signs	X	X 		
Toxicity assessment		X	X	X
Performance Status	X	X 	X	
CBC, Differential, Platelets 	X	X 	X 	
Creatinine, Electrolytes (K + , Na + , Cl  , CO 2 ), Mg ++ , Ca ++	X	X 	X 	
Liver enzymes 	X	X (every 3 weeks)	X	
PT/PTT 	X			
Chest X-ray	X			
Pregnancy test 	X			
HIV status obtained via history	X			
CT or MRI of the head/neck	X		X	X 
CT of the chest	X		X	X 
Bone scan, if clinically indicated	X			
Tumor measurements 	X		X	X 
PET scan (optional) 	X		X	X
Swallowing assessment 	X			X 
Dental evaluation	X			
Tumor Biopsy and correlatives 	X	X (after 2 weeks)		
ENT evaluation/endoscopy	X		X	

1. Complete blood counts with differential and platelet count should be performed.
2. Liver function tests should include: Bilirubin, AST (SGOT), ALT (SGPT), and alkaline phosphatase. LFTs are required at least every 3 weeks during treatment.
3. All females of childbearing potential must have a negative pregnancy test done within 3 days of initiation of treatment to rule out pregnancy.
4. Tumor measurements will be made using physical examination, including endoscopic examination (clinically) and CT scans or MRI scans (radiographically). Clinical and radiographic assessments will be reported separately. Response in the primary and the neck will be reported separately as well. Tumor assessments will be performed 6-8 weeks after completion of radiotherapy. Subsequently, repeat imaging with CT scans of chest and head and neck will be performed every 3 months for 1 year and then every 6 months for a total of 3 years from the time of radiation completion. Then, CT of the chest or chest x-ray will be done on an annual basis.
5. Positron emission tomography (PET) scan or combined PET/CT scanning is optional. Results will be reported separately.
6. Swallowing assessments will be performed at baseline and 3 months post radiation completion, and if problems persist, at 12 months post radiation.
7. The following materials will be submitted: fresh frozen and paraffin-embedded tumor specimens for molecular studies.
8. Patients will be followed every 3 months for 2 years and then every 6 months for 3 years, and subsequently annually for a total of 10 years from study initiation.

9. During radiation, in the immediate 2 week period following RT completion, and the 6-10 week follow-up after RT completion; patients need a focused evaluation of toxicities on a weekly basis. However, a complete history and physical examination is only needed every 3 weeks.
10. PT/PTT will be performed at baseline while the patient is receiving intratumoral injections or more frequent, if clinically indicated.
11. All patients should be seen by a Medical Oncologist, an ENT surgeon, and a Radiation Oncologist prior to initiating therapy. Unresectability should be determined by a multidisciplinary team.

## 10. DRUG FORMULATION AND PROCUREMENT

### 10.1 EGFR Antisense

EGFR antisense DNA is plasmid DNA and will be prepared under conditions consistent with cGMP as described in CFR 210 and 211. Production will occur in the Center for Biomedicine and Genetics, the National Gene Vector Laboratory (NGVL) designated site at the Beckman Research Institute of the City of Hope in Duarte, California, under the direction of [name]. Manufacturing and quality release testing will be performed as described in BB-MF 9778 (see cross reference authorization letter provided as an attachment).

#### Drug Information

#### Production of Plasmid DNA

Plasmid DNA was produced under GMP conditions at the Center for Biomedicine and Genetics (CBG) at the City of Hope according to City of Hope's Master File BB-MF-9778. Briefly, a bacterial Master Cell bank was produced in the STBLII competent cell line. Bacteria from the tested and released Master Cell Bank was used to inoculate "starter" and expansion cultures to seed 6 liter batches in a New Brunswick BioFlo3000 fermentor using proprietary bacterial media optimized for plasmid DNA production. The 6 liter culture was grown at 35°C for 20 -4 hours with automated (PID loop) temperature, aeration and pH adjustment. Following fermentation the culture was harvested and bacterial pellets stored at -20°C for further processing.

Bacteria were processed using a modified alkaline lysis method (Birnboim, H.C. and Doly, J.(1979) Nucl. Acids. Res. 7,1513-1522). Briefly, bacterial pellets are resuspended in 50mM Tris-Cl, 10mM EDTA and then lysed with an equal volume of 200mM NaOH, 1% SDS at room temperature. The lysate is neutralized with 3.0M potassium acetate and clarified by centrifugation to remove the bulk of proteins, lipid and bacterial genomic DNA. The clarified lysate is passed through a series of filters (50 · 0.2 ) and then concentrated 10-fold to 15-fold over a 30,000 NMWCO PES ultrafiltration device (Millipore ProFlux M12/Pellicon system). At this stage the concentrated lysate was held for 24 hours at 4°C.

Concentrated lysate was further clarified using depth filtration in the presence of filter aid and RNA removal was achieved by size exclusion chromatography over Sepharose 6 Fast Flow · (GE Healthcare). Plasmid DNA devoid of RNA contaminants was treated with an endotoxin adsorbent to remove trace endotoxin contamination. The plasmid DNA was concentrated and reformulated into PBS using tangential flow filtration. Samples of the bulk material were taken for release testing with the balance of the material stored at -20 C. The bulk material that met the defined specifications for protein, endotoxin, RNA and contaminating bacterial genomic

DNA were thawed and pooled for fill and finish.

Final fill of the plasmid DNA was preceded by end-point sterilization through a 0.2 µm filter. Final product vials were transferred to Quality Assurance who coordinated final product testing and shipment of released material.

### EGFR Antisense Shipping

EGFR antisense DNA is plasmid DNA, and is considered to be Biohazard I (BSL-1) since it does not contain viral elements, toxic proteins or oncogenes and will be shipped and handled as a research reagent as per biohazard material guidelines. The product will be supplied vialled and formulated in 1-2 mg/mL concentrations, stored at -80 °C, and shipped on dry ice. Based on ICH recommendations, the product must be used within 3 hours from thawing of the product. Any/all unused product will be returned to the NGVL. EGFR antisense DNA will be sent from the University of Pittsburgh Pharmacy to our site's Investigational Drug Section (IDS). It will be shipped on dry ice for overnight delivery (Monday-Thursday). Upon arrival at IDS, drug will be inspected to ensure its intact/undamaged during shipping.

## 10.2 Cetuximab (C225, ERBITUX)

Cetuximab is an anti-EGFR human-to-murine chimeric antibody. Cetuximab is expressed in SP2/0 myeloma cell line, grown in large scale cell culture bioreactors and purified to a high level purity using several purification steps including protein A chromatography, ion exchange chromatography, low pH treatment and nanofiltration. Cetuximab is not known to be a vesicant.

### Supplier/How Supplied

Cetuximab is commercially available. The product is a sterile, clear, colorless liquid of pH 7.0 to 7.4, which may contain a small amount of easily visible, white, amorphous cetuximab particulates. Each single-use 50-mL vial contains 100 mg of cetuximab at a concentration of 2 mg/mL and is formulated in a preservative-free solution containing 8.48 mg/mL sodium chloride, 1.88 mg/mL sodium phosphate dibasic heptahydrate, 0.42mg/mL sodium phosphate monobasic monohydrate, and Water for injection, USP.

### Packaging and Labeling

Cetuximab is supplied as a 50mL, single-use vial containing 100mg of Cetuximab at a concentration of 2mg/mL in phosphate buffered saline. The solution should be clear and colorless and may contain a small amount of easily visible white amorphous Cetuximab particulates.

### Storage Requirement/Stability

Store vials under refrigeration at 2°C to 8°C (36°F to 46°F). DO NOT FREEZE. Increased particulate formation may occur at temperatures at or below 0°C. This product contains no preservatives. Preparations of cetuximab in infusion containers are chemically and physically stable for up to 12 hours at 2°C to 8°C (36°F to 46°F) or up to 8 hours at controlled room temperature (20°C to 25°C; 68°F to 77°F). Discard any remaining solution in the infusion container after 8 hours at controlled

room temperature or after 12 hours at 2 to 8 C. Discard any unused portion of the vial.

#### Preparation and Administration

Cetuximab must not be administered as an IV push or bolus.

Cetuximab must be administered with the use of a low protein binding 0.22-micrometer in-line filter.

Cetuximab is supplied as a 50-mL, single-use vial containing 100 mg of cetuximab at a concentration of 2 mg/mL in phosphate buffered saline. The solution should be clear and colorless and may contain a small amount of easily visible white amorphous cetuximab particulates. DO NOT SHAKE OR DILUTE.

Cetuximab can be administered via infusion pump or syringe pump.

#### Infusion Pump:

- Draw up the volume of a vial using a sterile syringe attached to an appropriate needle (a vented spike or other appropriate transfer device may be used).
- Fill cetuximab into a sterile evacuated container or bag such as glass containers, polyolefin bags (eg, Baxter Intravia), ethylene vinyl acetate bags (eg, Baxter Clintec), DEHP plasticized PVC bags (eg, Abbott Lifecare), or PVC bags.
- Repeat procedure until the calculated volume has been put in to the container. Use a new needle for each vial.
- Administer through a low protein binding 0.22-micrometer in-line filter (placed as proximal to the patient as practical).
- Affix the infusion line and prime it with cetuximab before starting the infusion.
- Maximum infusion rate should not exceed 5 mL/min.
- Use 0.9% saline solution to flush line at the end of infusion.

#### Syringe Pump:

- Draw up the volume of a vial using a sterile syringe attached to an appropriate needle (a vented spike may be used).
- Place the syringe into the syringe driver of a syringe pump and set the rate.
- Administer through a low protein binding 0.22-micrometer in-line filter rated for syringe pump use (placed as proximal to the patient as practical).
- Connect up the infusion line and start the infusion after priming the line with cetuximab.
- Repeat procedure until the calculated volume has been infused.
- Use a new needle and filter for each vial.
- Maximum infusion rate should not exceed 5 mL/min.

- Use 0.9% saline solution to flush line at the end of infusion.
- Cetuximab should be piggybacked to the patient's infusion line.

Following the cetuximab infusion, a 1-hour observation period is recommended.

#### Safety Precautions:

Appropriate mask, protective clothing, eye protection, gloves, and Class II vertical-laminar-airflow safety cabinets are recommended during preparation and handling. Opened vials must be disposed of at the investigational center as chemotherapy or biohazardous waste provided documented procedures for destruction are in place. For questions regarding cetuximab destruction please contact BMS at [contact] or [contact].

Cetuximab therapy should be used with caution in patients with known hypersensitivity to Cetuximab, murine proteins, or any component of this product.

It is recommended that patients wear sunscreen and hats and limit sun exposure while receiving cetuximab as sunlight can exacerbate any skin reactions that may occur.

#### Cetuximab Records at Investigational Site(s)

It is the responsibility of the Investigator to ensure that a current record of investigational product disposition is maintained at each study site where investigational product is inventoried and disposed. Records or logs must comply with applicable regulations and guidelines, and should include:

- Amount received and placed in storage area.
- Amount currently in storage area.
- Label ID number or batch number.
- Dates and initials of person responsible for each investigational product inventory entry/movement.
- Amount dispensed to and returned by each patient, including unique patient identifiers.
- Amount transferred to another area for dispensing or storage.
- Non-study disposition (e.g., lost, wasted, broken).

#### Drug Ordering and Accountability

The ordering and drug accountability for Cetuximab will be handled per institutional Standard Operating Procedures (SOPs).

It is the responsibility of the Investigator to ensure that a current record of study drug disposition is maintained at each study site where the study drug is inventoried and

disposed. Records or logs must comply with applicable regulations and guidelines.

#### Nursing Implications

Patients need monitoring for infusion reactions. Premedication with diphenhydramine hydrochloride [Benadryl] will be used as described in Sections 5.0 and 5.1.

Diarrhea is a possible side effect of cetuximab. It can be managed with loperamide (Imodium).

## 11. STATISTICAL CONSIDERATIONS

### 11.1 Primary Endpoint

This is a 2-stage clinical trial. In the first stage, toxicity will be the primary endpoint. In the second stage (phase II component), the primary endpoint will be the locoregional progression free survival (PFS) at 1 year. Toxicities will also be evaluated during the second stage using continuous Bayesian monitoring as described below.

Sample size for the primary objective: 11 evaluable patients (stage 1); 31 evaluable patients (stage 2)

First stage: 11 evaluable patients. The safety-evaluable population for stage 1 consists of all patients who either complete the treatment regimen or withdraw from study by reason of toxicity.

Toxicities due to EGFR AS in our previous phase I trial were negligible, and consisted of grade 1 injection site pain and swelling. Because we will combine EGFR AS with radiation and cetuximab in the proposed clinical trial, a separate safety evaluation will be conducted. In the first stage (safety component), 11 patients will be treated and observed for serious adverse events (SAEs) that are due to EGFR AS (possibly, probably, or definitely), not cetuximab or radiation. In the first stage, after three (3) subjects are enrolled and have received all EGFR AS injections, there will be a two-week waiting period to assess adverse events. After the two-week period, additional subjects may be enrolled. Eligible patients will include stage IV or recurrent patients who would not be eligible for the subsequent study of efficacy, and their accrual to study is only for the assessment of safety. We seek to rule out an SAE rate of 20% or greater due to EGFR AS. If no grade 3/4 toxicities due to EGFR AS are observed among 11 patients, then an upper 90% confidence bound for the SAE rate is less than 20%.

Second stage (phase II component): 31 evaluable patients. The efficacy-evaluable population consists of all patients who complete the treatment regimen.

Sample size for the second stage of study is based on the primary endpoint: 1-year locoregional PFS. We use a historical control rate of 63% for 1-year locoregional PFS in patients on radiation and cetuximab, as reported by Bonner et al. To account for the inherent variability in this estimate, and to improve the likelihood that we can detect a true improvement with the addition of EGFR AS, we use the reasoning of Fazzari et al. which advocates setting the null hypothesis to the upper bound of the 75 percent confidence interval for the historical-control endpoint. By assuming that 1-year locoregional PFS as reported by Bonner et al follows an exponential distribution from a

sample of 211 patients, the upper 75th percent confidence bound for 1-year locoregional PFS is 68%. Targeting a 50% reduction in the hazard rate for 1-year locoregional PFS under our treatment regimen implies that 1-year locoregional PFS would be improved to 83%. To achieve this objective, we plan a study with 2 years of patient accrual, 1 year of additional follow-up, and assume that 1-year locoregional PFS will have an exponential distribution. Under these assumptions, a 1-sided exponential test at  $\alpha = 0.10$  will provide 90% power with 31 patients. In addition, we plan to evaluate tumor response and locoregional progression in injected and non-injected lymph nodes. The rates of progression in injected versus non-injected regions will be compared by an exact test for two rates, implemented in StatXact 8.

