#### Dose/Schedule Modifications

There will be no dose reductions. However, weekly doses will be omitted in the setting of locoregional toxicities (even if those are thought to be related to radiation).

Based on prior experience, the expected toxicities of EGFR AS therapy may include local discomfort at the injection site, edema, bleeding and cutaneous erythema when the treatment is administered.

Treatment with EGFR AS will be held in the setting of grade 3 or 4 mucositis/dermatitis.

Treatment with EGFR AS will be discontinued if there is cellulitis at the injection site requiring antibiotic therapy or grade 4 locoregional toxicities within the injected site develop (such as bleeding or tissue necrosis).

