### **Total sample size**

A total of 42 evaluable patients will be accrued to study.

Eleven patients will be treated in the first stage, which will assess the safety of the combination. Patients failing to complete treatment for reasons other than toxicity will be replaced.

In the second stage, 31 efficacy-evaluable patients will be enrolled, provided safety is acceptable.

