## 11.6 Additional Analyses

The data from all evaluable patients will be used in the analyses of safety (phase I and phase II), tumor response (phase II), and survival (phase II).

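### The stage 1 safety set is defined by the reason for stopping, so a grade 3/4 EGFR AS event in a patient who later leaves for another reason drops out of the 0-of-11 count

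*Combined protocol and SAP*

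**What the plan says.** Toxicity is the primary endpoint of the first stage (Section 11.1). The stated aim is "We seek to rule out an SAE rate of 20% or greater due to EGFR AS", and events possibly, probably or definitely due to EGFR AS count. The sample size rests on a zero-event result. For that outcome the section states that "an upper 90% confidence bound for the SAE rate is less than 20" per cent.

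The denominator is restricted: "The safety-evaluable population for stage 1 consists of all patients who either complete the treatment regimen or withdraw from study by reason of toxicity". Under Total sample size, the plan adds: "Patients failing to complete treatment for reasons other than toxicity will be replaced".

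Three other places bear on how this works:

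- Section 5.2, Dose/Schedule Modifications: "Treatment with EGFR AS will be held in the setting of grade 3 or 4 mucositis/dermatitis". Such an event therefore interrupts the injections and does not in itself end participation.
- Section 7.8 lists the reasons for removal from study. They include progression, the patient's decision and the investigator's judgment, as well as unacceptable adverse events.
- Section 11.6 opens with "The data from all evaluable patients will be used in the analyses of safety (phase I and phase II"). Its Safety Profile paragraph, however, speaks of patients with adverse events over their course of treatment plus 30 days, and of reporting the details of all treatment-related toxicities, without repeating the restriction to evaluable patients.

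**The concern.** Where toxicity is the endpoint, a patient's event should count because it happened. Here it counts only if the patient finishes the regimen or leaves because of toxicity. A patient can have a grade 3 event judged possibly due to EGFR AS, have injections held, stay on study, and then leave for progression or by choice. That patient meets neither condition and is replaced. A death on treatment not attributed to toxicity is in the same position.

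At stake is the only quantitative safety statement made before 31 previously untreated patients receive the combination with curative intent. The statement is valid only if every exposed patient's qualifying event enters the count.

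**Working it through.** **Inputs from the documents.** n = 11 evaluable patients, 0 events, rate to be excluded 20%, upper 90% bound (all Section 11.1).

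**Inputs not in the documents.** The proportions of patients with and without an event who leave for non-toxicity reasons. These are assumed below.

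**1. Reproduce the plan's figure.** The exact one-sided upper bound for 0/n is 1 − 0.10^(1/n).

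- n = 11: 1 − 0.10^(1/11) = 18.9%, below 20% as stated.
- n = 10: 20.6%.

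Eleven is therefore the smallest n that works, and there is no slack. The 95% one-sided version gives 23.8%, so the plan's bound is a one-sided 90% bound. At a true rate of 20%, the chance of seeing 0/11 is 0.8^11 = 8.6%.

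**2. One event in a replaced patient.** Suppose 11 evaluable patients are event-free and a twelfth treated patient had a qualifying event, left for a non-toxicity reason and was replaced. The formal result is 0/11, bound 18.9%. With all treated patients counted it is 1/12. Taking 12 as fixed, the exact bound solves (1 − p)^12 + 12p(1 − p)^11 = 0.10, which gives p = 28.7%. With two such patients the result is 2/13, bound 36.0%. With one event, at least 18 patients are needed before the bound falls below 20%. This step needs no assumption about leaving rates.

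**3. Effect on the chance of a zero-event result.** Let p = 0.20 be the true event rate, q the share of patients with an event who leave for a non-toxicity reason, and d the same share among event-free patients. The event rate among counted patients is

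p(1 − q) / [p(1 − q) + (1 − p)(1 − d)],

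and the chance of 0/11 is (1 − that rate)^11.

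| q (assumed) | d = 0: rate counted | d = 0: P(0/11) | d = 10%: rate counted | d = 10%: P(0/11) |
|---|---|---|---|---|
| 10% | 0.18/0.98 = 18.4% | 10.7% | 0.18/0.90 = 20.0% | 8.6% |
| 25% | 0.15/0.95 = 15.8% | 15.1% | 0.15/0.87 = 17.2% | 12.5% |
| 50% | 0.10/0.90 = 11.1% | 27.4% | 0.10/0.82 = 12.2% | 23.9% |

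When q = d the counted rate stays at 20% and the probability stays at 8.6%. Inflation requires q to exceed d.

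**The case against.** **The loss may be neutral.** If progression or personal choice removes patients with and without events at the same rate, the long-run error is unchanged. That is correct. A reader might infer that the rule necessarily pushes the error above 10%. The table does not support that: it depends on differential leaving, for which the documents give no figure. Nor do they show that early leaving will be common in stage 1. Section 3.1 limits patients with M1 disease to those with asymptomatic or low-volume metastases.

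**The route is narrow.** Patients who leave because of the event are counted. The hold rule concerns mucositis and dermatitis, which Section 11.4 reports at 56% and 23% (grade 3/4) on radiation plus cetuximab, whereas stage 1 counts only events due to EGFR AS. Section 5.2 discontinues EGFR AS for grade 4 toxicity within the injected site. What remains is a held event judged at least possibly due to EGFR AS, followed by exit for another stated reason. This is narrower than all grade 3/4 toxicity, but nothing in the plan closes it.

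**Stage 2 does not open by a mechanical rule.** A reader might infer that 0/11 automatically opens stage 2. The abstract and Total sample size make it depend on a judgment that the regimen is safe or its safety acceptable. Sections 6.3 and 6.4 put adverse events before the principal investigator and DSMB #2 quarterly, and the expedited-reporting table in Section 6 covers deaths within 30 days of the last dose whatever the attribution. Reviewers would probably see such an event. This lowers the risk of a wrong decision, but it does not put the event back into the count behind the 20% claim.

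**The final tables may include the event.** A reader might infer that it also disappears from the final safety tables. The text is unclear: the opening sentence of Section 11.6 points one way and its Safety Profile paragraph the other.

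**Conclusion.** The point holds as a defect in the counting rule. Sections 11.1 and 5.2 and the removal reasons in Section 7.8 together allow a qualifying event to be left out of the stage 1 numerator and denominator, and no other section restores it. The plan does not say that events are discarded. This follows from a definition that has no exception for an earlier event.

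A single such case is enough to reverse the stated conclusion: 0/11 with a bound of 18.9% becomes 1/12 with a bound of 28.7%. How often this would mislead is unknown. Under the assumed leaving rates, the chance of 0/11 at a true 20% rate runs from 8.6% (no inflation) to 27.4%. The upper values require patients with an event to leave for non-toxicity reasons much more often than others. That is possible, since a patient with a severe event may choose to stop and the recorded reason involves judgment, but the documents neither show nor quantify it.

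Given the narrow route, the neutral case with no inflation and the independent oversight, this is a should-fix point.

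**What to change.** - **Section 11.1.** State that any qualifying grade 3/4 event at least possibly due to EGFR AS counts toward the stage 1 result if it occurs in any stage 1 patient given at least one EGFR AS injection, whatever the reason for stopping. The section uses both SAE and grade 3/4 toxicity for the event, so say which one qualifies.
- **Total sample size.** Keep replacement only as a means of reaching 11 patients with full exposure, with replaced patients retained in the event count. State what counts as completing the regimen when EGFR AS doses have been omitted under Section 5.2, since the safety set turns on it.
- **Section 11.6.** State that safety is reported on all treated patients in both stages.

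The cost is wording. No extra patients, visits or procedures are needed, and no treatment rule changes. The downside is that stage 1 may give a less favourable result: one qualifying event among 12 treated patients would no longer support the claim that a 20% rate has been excluded.
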